## 6.2 IMPORTANT PROTOCOL DEVIATIONS

Data discrepancies and deviations from the CTP will be identified for all treated subjects.

Consistency check listings (for identification of deviations of time windows) and a list of protocol deviations (e.g. deviations in drug administration, in blood sampling times, etc.) will be provided to be discussed at the Report Planning Meeting (RPM). At this meeting, all manual deviations identified at the sites by the CRAs and deviations too complex to program will be reviewed by the trial team to decide which are considered important. For definition of important protocol deviations (iPD), and for the process of identification of these, refer to the Boehringer Ingelheim (BI) SOP "Identify and Manage Important Protocol Deviations (iPD)" (2).

**Section 7.3 of the CTP:** *Important protocol deviation (IPD) categories will be specified in the iPD specification file prior to trial initiation, IPDs will be identified no later than in the Report Planning Meeting, and the IPD categories will be updated as needed.*

If any iPDs are identified, they are to be summarised into categories and will be captured in the iPD specification file and the decision log. The iPD specification file (e.g. the DV domain specifications) will be stored within the TMF in EDMS.

The iPDs will be summarized and listed in the CTR.

## 6.3 SUBJECT SETS ANALYSED

### **Section 7.3 of the CTP:**

- *Treated set (TS):*  
*The treated set includes all entered subjects who were treated with one dose of study drug (i.e. verum or placebo). The treated set will be used for safety analyses.*
- *Pharmacokinetic parameter analysis set (PKS):*  
*This set includes all subjects in the treated set (TS) who provide at least one PK endpoint that was defined as primary or secondary and was not excluded due to a protocol deviation relevant to the evaluation of PK or due to PK non-evaluability (as specified in the following subsection 'Pharmacokinetics'). Thus, a subject will be included in the PKS, even if he/she contributes only one PK parameter value to the statistical assessment. Descriptive and model based analysis of PK parameters will be based on the PKS.*
- *Pharmacodynamic parameter analysis set (PDS):*  
*This set includes all evaluable subjects from the TS who provide at least one evaluable pre- and post-dose measure for a PD endpoint. Descriptive and model based analysis of the PD endpoints will be based on the PDS.*

In addition to the analysis sets defined in the CTP, the following set of subjects will be used in the analysis:

### Section 7.3 of the CTP:

#### Pharmacokinetics

*The pharmacokinetic parameters listed in CTP Section 2.1 and 2.2 for drug BI 474121 will be calculated according to the relevant BI internal procedures.*

*Plasma and CSF concentration data and parameters of a subject will be included in the statistical pharmacokinetic (PK) analyses if they are not flagged for exclusion due to a protocol deviation relevant to the evaluation of PK (to be decided no later than in the Report Planning Meeting) or due to PK non-evaluability (as revealed during data analysis, based on the criteria specified below). Exclusion of a subject's data will be documented in the CTR.*

*Relevant protocol deviations may be*

- *Incorrect trial medication taken, i.e. the subject received at least one dose of trial medication the subject was not assigned to*
- *Incorrect dose of trial medication taken*
- *Use of restricted medications*

*Plasma and CSF concentrations and/or parameters of a subject will be considered as non-evaluable, if for example*

[figure not shown]
- *The subject experienced emesis that occurred at or before two times median  $t_{max}$  of the respective treatment (Median  $t_{max}$  is to be determined excluding the subjects experiencing emesis)*
- *Missing samples/concentration data at important phases of PK disposition curve*

*Plasma and CSF concentration data and parameters of a subject which is flagged for exclusion will be reported with its individual values but will not be included in the statistical analyses. Descriptive and inferential statistics of PK parameters will be based on the PKs.*

The same criteria will be considered regarding PD concentrations and/or parameters for evaluability.

Table 6.3: 1 Subject sets analysed

Class of endpoint	Subject analysis set			
	TS	PKS	PDS	PDS-sens
Analyses of PK endpoints		X		
Analyses of PD endpoints			X	X
Disposition	X			
Demographic/baseline parameters	X			
Important protocol deviations	X			
Exposure	X			

## 6.5 POOLING OF CENTRES

This section is not applicable, because the study was performed in only one centre.

## 6.6 HANDLING OF MISSING DATA AND OUTLIERS

Handling of missing data and outliers will be performed as described in the CTP, Section 7.5.

The only exceptions where imputation might be necessary for safety evaluation are AE dates. Missing or incomplete AE dates are imputed according to BI standards (see BI-KMED-BDS-HTG-0035) (3).

Missing data and outliers of PK data are handled according to BI standards (see BI-KMED-TMCP-MAN-0012 (4) and BI-KMED-TMCP-MAN-0014 (5)).

## 6.7 BASELINE, TIME WINDOWS AND CALCULATED VISITS

The baseline value is generally defined as the last measurement before administration of trial medication (BI 474121 or Placebo).

The baseline cGMP concentration ( $cGMP_{base}$ ) is defined in **Section 7.3.1 of the CTP**:

*The baseline cGMP value of a subject is defined as the arithmetic mean of all pre-dose measurements above LLOQ (lower limit of quantification) obtained in that subject. In case all three values are BLQ (below limit of quantification), the LLOQ of the bioanalytical assay will be used as baseline value.*

**Section 6.1 of the CTP:**

*Exact times of measurements outside the permitted time windows will be documented. The acceptable time windows for screening and the end of trial examination are provided in the CTP Flow Chart.*

*Study measurements and assessments scheduled to occur 'before' trial medication administration on Day 1 are to be performed and completed within a 3 h-period prior to the trial drug administration.*

*The acceptable deviation from the scheduled time for vital signs, ECG, and sample collection for laboratory tests will be  $\pm 30$  min.*

Adherence to time windows will be checked via the consistency check listings at the RPM. Unscheduled measurements of laboratory data and vital signs data will be assumed to be repeat measurements of the most recent scheduled measurement (e.g. for follow-up or confirmation of a particular value). Therefore, unscheduled measurements will be assigned to the planned time point of the previous scheduled measurement.

## 7. PLANNED ANALYSIS

If not stated otherwise, the trial parts will be evaluated together. Outputs will be sorted by treatment group (Placebo, BI 2.5mg, BI 10mg, BI 20mg, BI 40mg).

Safety analysis (refer to [Section 7.8](#)) will be performed by [REDACTED] and will be presented in Sections 15.1 to 15.4 of the CTR and in Appendix 16.2 and 16.1.13.1.

Statistical model-based analysis of PK and PD endpoints will be performed by [REDACTED] and will be presented in Section 15.5 of the CTR and in Appendix 16.1.13.3.

Descriptive data analysis of PK endpoints and concentrations will be performed by the [REDACTED] at [REDACTED] and will be presented in Section 15.6 of the CTR and in Appendix 16.1.13.5.

Descriptive data analysis of PD/biomarker parameters will be performed by the [REDACTED] at [REDACTED] and will be presented in Section 15.7 of the CTR and Appendix 16.1.13.6.

The format of the listings and tables will follow the BI standards (see BI-KMED-BDS-HTG-0045 (6)) with the exception of those generated for PK-calculations following BI standards for PK/PD analysis (7).

The individual values of all subjects will be listed, sorted by treatment group, subject number and visit.

The listings will be included in Appendix 16.2 of the CTR.

For end-of-text tables, the set of summary statistics for non-PK and non-PD parameters is:

N	number non-missing observations
Mean	arithmetic mean
SD	standard deviation
Min	minimum
Median	median
Max	maximum

For analyte concentrations, the following descriptive statistics will additionally be calculated:

CV	arithmetic coefficient of variation
gMean	geometric mean
gCV	geometric coefficient of variation

For PK and PD parameters, the following descriptive statistics will additionally be calculated:

CV	arithmetic coefficient of variation
gMean	geometric mean
gCV	geometric coefficient of variation
P10	10th percentile
Q1	1st quartile
Q3	3rd quartile
P90	90th percentile

The data format for descriptive statistics of concentrations will be identical to the data format of the respective concentrations. The descriptive statistics of PK and PD parameters will be calculated using the individual values with the number of decimal places as provided by the evaluation program. Then the individual values as well as the descriptive statistics will be reported with three significant digits in the CTR.

Tabulations of frequencies for categorical data will include all possible categories and will display the number of observations in a category, as well as the percentage (%). Percentages will be rounded to one decimal place and will be based on all subjects in the respective subject set whether they have non-missing values or not. The category 'missing' will be displayed only if there are actually missing values.

Units of variables should be given in the titles or column/row descriptors in brackets (e.g. (mg)).

#### Exclusion of PK and PD parameters

The ADS “ADPP” (PK parameters) or “ADYP” (PD parameters) contains column variables APEXC and APEXCO indicating inclusion/exclusion (APEXC) of a PK or PD parameter and an analysis flag comment (APEXCO). All analyses based on the PKs and PDS, respectively, will include parameters if they are not flagged for exclusion, that is APEXC is equal to “Included”.

#### Exclusion of PK and PD concentrations

The ADS “ADPC” (PK concentrations per time-point or per time-interval) or “ADYC” (PD concentrations per time-point or per time-interval) contains column variables ACEXC and ACEXCO indicating inclusion/exclusion (ACEXC) of a concentration and an analysis flag comment (ACEXCO). Exclusion of a concentration depends on the analysis flag comment ACEXCO. For example, if ACEXCO is set to ‘ALL CALC’, the value will be excluded for all types of analyses based on concentrations. If ACEXCO is set to ‘DESC STATS’ the value will be excluded from descriptive evaluations per planned time point/time interval. If ACEXCO contains the addition ‘TIME VIOLATION’ or ‘TIME DEVIATION’ the value can be used for further analyses based on actual times. If ACEXCO is set to ‘HALF LIFE’, the value will be excluded from half-life calculation (and, as a consequence, any calculation that relies on  $\lambda_z$ ) only; the value is included for all other analyses.

Further details are given in *BI-KMED-TMCP-MAN-0014* “Noncompartmental Pharmacokinetic / Pharmacodynamic Analyses of Clinical Studies” (5) and *BI-KMED-TMCP-MAN-0010*: “Description of Analytical Transfer Files and PK/PD Data Files” (8).

### Interim analyses

No inferential statistical interim analysis is planned. Preliminary analyses of safety, PK and PD parameters were performed after trial part 1 and 2 (including  $C_{max}$  and  $AUC_{0-24}$  of BI 474121 in plasma and cGMP in CSF). The preliminary analyses after Part 1 and 2 were done to evaluate the proof-of-pharmacological-principal for BI 474121. Furthermore a preliminary analysis after Part 3 (PK and PD only) will be done to support dose finding for trial 1411-0003. In contrast to the final PK and PD calculations, the preliminary analysis will be based on planned sampling times rather than on actual times. All details about the preliminary analyses are described in a trial-specific logistics plan (9).

## 7.1 DEMOGRAPHIC AND OTHER BASELINE CHARACTERISTICS

Only descriptive statistics are planned for this section of the report, based on the TS. The data will be summarised by treatment group and in total.

## 7.2 CONCOMITANT DISEASES AND MEDICATION

Frequency tables are planned for this section of the report, based on the TS.

Concomitant diseases will be coded using the coding system of the Medical Dictionary for Drug Regulatory Activities (MedDRA). Medications will be coded using the World Health Organization Drug Dictionary (WHO-DD). The coding version number will be displayed as a footnote in the respective output.

The diagnoses and medications will be listed. Subjects without any concomitant diagnoses or concomitant therapies should be marked with a “No” in the respective column.

The relevance of the concomitant therapies to the evaluation of PK will be decided no later than at the RPM.

## 7.3 TREATMENT COMPLIANCE

**Section 4.3 of the CTP:** *Compliance will be assured by administration of all trial medication in the study centre under supervision of the investigating physician or a designee. The measured plasma concentrations of trial medication will provide additional confirmation of compliance.*

It is not intended to list the compliance separately. Any deviations from complete intake will be addressed in the RPM (cf. TSAP [Section 6.2](#)) and described in the CTR.

## 7.4 PRIMARY ENDPOINTS

The final statistical analysis will include data from all trial parts. Additionally to the model-based analysis of the primary endpoints as described below, the primary endpoints will be analysed using descriptive statistics.

### 7.4.1 Primary analysis of the primary endpoints

#### 7.4.1.1 Analysis of first primary endpoint

##### Section 7.3.2 of the CTP:

##### Maximum exposure-related change from baseline of cGMP in CSF

The maximum exposure-related change from baseline in cGMP in CSF will be explored using an ANCOVA model, which can be described by the following equation:

$$y_{i,j} = \alpha \ln(\text{cGMP}_{\text{base},i}) + \text{treatment}_j + e_{i,j}$$

Where

$y_{i,j}$  = natural logarithm of the ratio  $\text{cGMP}_{\text{max},i}/\text{cGMP}_{\text{base},i}$  for subject  $i$  receiving treatment  $j$

$\alpha$  = slope parameter for the baseline effect

$\text{cGMP}_{\text{base},i}$  =  $\text{cGMP}_{\text{base}}$  for subject  $i$

$\text{treatment}_j$  = the  $j^{\text{th}}$  treatment effect, (placebo, 2.5mg, 10mg, 20 mg, 40mg)

$e_{i,j}$  = random error associated with  $i^{\text{th}}$  subject who received treatment  $j$

For the endpoint  $\text{cGMP}_{\text{max}}/\text{cGMP}_{\text{base}}$ , the difference between the expected means for  $\ln(T) - \ln(R)$  will be estimated by the difference in the corresponding least square means (point estimate) and two-sided 90% confidence intervals based on the  $t$ -distribution will be computed. These quantities will then be back-transformed to the original scale to give the point estimator and interval estimates.

Estimates will be computed for the different dose groups (T) versus placebo (R), respectively.

The analysis of the first primary endpoint will be performed on the PDS. The implementation for this analysis in SAS will be accomplished by using the MIXED procedure within the CSD macro %X\_TLF\_ANCOVA1:

```
PROC MIXED DATA=patdata CL METHOD=reml ORDER=data;  
  CLASS treatment (REF='Plc tab');  
  MODEL logpd = logbaseline treatment / SOLUTION;  
  LSMEANS treatment / CL DIFF ALPHA=0.1;  
RUN;
```

#### 7.4.1.2 Analysis of second primary endpoint

##### Cmax ratio of BI 474121 in CSF compared to plasma

The relationship between exposures of BI 474121 in CSF compared to plasma will be explored using a mixed effects model, which can be described by the following equation:

$$\ln(C_{\max_{i,j,k}}) = \text{subject}_i(\text{treatment}_j) + \text{treatment}_j + \text{pkmatrix}_k + e_{i,j,k}$$

where

$\text{subject}_i$  = the  $i^{\text{th}}$  subject effect, a random effect nested within treatment group  $j$   
 $\text{treatment}_j$  = the  $j^{\text{th}}$  treatment effect (2.5mg, 10mg, 20 mg, 40mg)  
 $\text{pkmatrix}_k$  = the  $k^{\text{th}}$  substance effect (CSF or plasma)  
 $e_{i,j,k}$  = random error associated with  $i^{\text{th}}$  subject who received treatment  $j$  in substance  $k$

The effect 'subject nested within treatment' will be considered random, while all other effects will be considered as fixed. The pharmacokinetic parameter  $C_{\max}$  will be log transformed (natural logarithm) prior to fitting the model. The difference between the expected means for  $\log(\text{CSF}) - \log(\text{plasma})$  will be estimated by the difference in the corresponding least square means (point estimate) and two-sided 90% confidence intervals based on the t-distribution will be computed. These quantities will then be back-transformed to the original scale to give an overall point estimator and interval estimates for the geometric mean of the ratio between exposure in CSF and exposure in plasma.

In further analyses, the mixed model (as outlined above) will be supplemented by an interaction term of treatment and PK matrix. This model will be used to derive estimates of exposure in CSF vs. plasma by treatment.

The analysis of the second primary endpoint will be performed on the PKS. The implementation for this analysis in SAS will be accomplished by using the PROC MIXED procedure:

(1) primary model:

```
PROC MIXED DATA=data METHOD=reml ORDER=data;  
  CLASS treatment subject pkmatrix;  
  MODEL logcmax = treatment pkmatrix;  
  RANDOM subject(treatment) /S;  
  LSMEANS pkmatrix / CL DIFF ALPHA=0.10;  
  ODS OUTPUT lsmeans=lsmeans diffs=diffs;  
RUN;
```

(2) model for estimates by treatment group:

```
PROC MIXED DATA=data METHOD=reml ORDER=data;  
  CLASS treatment subject pkmatrix;  
  MODEL logcmax = treatment pkmatrix treatment*pkmatrix;  
  RANDOM subject(treatment) /S;  
  LSMEANS treatment*pkmatrix / SLICE=treatment CL DIFF ALPHA=0.10;  
  ODS OUTPUT slices=slices lsmeans=lsmeans diffs=diffs;  
RUN;
```

[REDACTED]

## 7.5 SECONDARY ENDPOINTS

[figure not shown]
### 7.5.1 Key secondary endpoints

This section is not applicable as no key secondary endpoint has been specified in the protocol.

### 7.5.2 (Other) Secondary endpoints

The analysis of secondary endpoints will be performed as defined in the CTP, i.e. using descriptive statistics.

[REDACTED]

## **7.7 EXTENT OF EXPOSURE**

Descriptive statistics are planned for this section of the report based on the TS. The date and time of drug administration will be listed for each subject.

## 7.8 SAFETY ANALYSIS

All safety analyses will be performed on the TS.

The safety data for treated subjects who failed to complete the study (dropouts or withdrawals) will be reported as far as their data are available. All withdrawals will be documented and the reason for withdrawal recorded.

### 7.8.1 Adverse Events

AEs will be coded with the most recent version of MedDRA.

Unless otherwise specified, the analyses of AEs will be descriptive in nature. All analyses of AEs will be based on the number of subjects with AEs and NOT on the number of AEs. BI standards as presented in “Analysis and Presentation of Adverse Event Data from Clinical Trials – Display Template” [BI-KMED-BDS-HTG-0041] (10) and [BI-KMED-BDS-HTG-0066] (11) will be applied.

The analysis of AEs will be based on the concept of treatment emergent AEs. That means that all AEs will be assigned to ‘screening’, ‘on-treatment’ or ‘follow-up’ phases as defined in [Section 6.1](#). AEs will be analysed based on actual treatments, as defined in [Table 6.1: 1](#).

According to the clinical study protocol, adverse events of special interest (AESI) will be analysed:

**Section 5.2.5.1.4 of the CTP:** *The following are considered as AESIs:*

- Hepatic injury  
*A hepatic injury is defined by the following alterations of hepatic laboratory parameters:*
  - o *An elevation of AST (aspartate transaminase) and/or ALT (alanine transaminase)  $\geq 3$ -fold ULN combined with an elevation of total bilirubin  $\geq 2$ -fold ULN measured in the same blood sample, or*
  - o *Aminotransferase (ALT, and/or AST) elevations  $\geq 10$  fold ULN*

According to ICH E3 (12), in addition to Deaths and Serious Adverse Events, ‘other significant’ AEs need to be listed in the clinical trial report. These will be any non-serious adverse event that led to an action taken with study drug (e.g. discontinuation or dose reduced or interrupted).

An overall summary of AEs will be presented.

The frequency of subjects with AEs will be summarised by treatment, primary system organ class (SOC) and preferred term (PT). Separate tables will be provided for subjects with serious AEs, for subjects with drug-related AEs, for subjects with drug-related serious adverse events and for subjects with AESIs. In addition, the frequency of subjects with AEs will be summarised by treatment, worst intensity, primary system organ class (SOC) and preferred term (PT).

The system organ classes will be sorted by default alphabetically, PTs will be sorted by frequency (within SOC). The MedDRA version number will be displayed as a footnote in the respective output.

In addition, frequencies of subjects with non-serious AEs that had an incidence of > 5% for at least one treatment will be summarised by treatment, primary SOC and PT.

For disclosure of adverse events on EudraCT, additional information not included in a standard AE analysis will be performed. The following three entries will be created:

- Adverse Events per arm for disclosure on EudraCT
- Non-serious Adverse Events for disclosure on EudraCT
- Serious Adverse Events for disclosure on EudraCT

### **7.8.2 Laboratory data**

The analyses of laboratory data will be descriptive in nature and will be based on BI standards [BI-KMED-BDS-HTG-0042] (13).

Laboratory data will be analysed qualitatively via comparison of laboratory data to their reference ranges. Values outside the reference range as well as values defined as possibly clinically significant will be flagged in the data listings.

Clinically relevant findings in laboratory data will be reported as baseline conditions (at screening) or as AEs (during the trial) if judged clinically relevant by the investigator, and will be analysed as such.

It is the investigator's responsibility to decide whether a lab value is clinically significantly abnormal or not (at the RPM at the latest).

Descriptive statistics of laboratory data including change from baseline will be calculated by planned time point based on the worst value of the subject at that planned time point (or assigned to that planned time point).

### **7.8.3 Vital signs**

Descriptive statistics over time including change from baseline will be performed for vital signs (blood pressure and pulse rate). In the listing the difference from baseline will also be displayed.

For vital signs, descriptive statistics will be calculated by planned time point based on the last value of the subject at that planned time point (or assigned to that planned time point).

Clinically relevant findings in vital signs will be reported as AEs.

#### **7.8.4 ECG**

ECG recordings were checked by the investigator for pathological results. Clinically relevant abnormal findings for ECG will be listed under 'Relevant Medical History / Baseline Conditions' (when they occurred during screening) or will be reported as AEs (when they occurred during treatment), and will be analysed as such. No separate ECG listing will be provided.

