#### 2.2.2.2 Safety and tolerability

Safety and tolerability of BI 474121 will be assessed based on:

- Adverse events (including clinically relevant findings from the physical examination)
- Safety laboratory tests
- 12-lead ECG
- Vital signs (blood pressure, pulse rate)

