#### 5.2.4 Electrocardiogram

Twelve-lead ECGs (I, II, III, aVR, aVL, aVF, V1 - V6) will be recorded using a computerised electrocardiograph system Marquette 800/2000/5500 or Dash 3000 at the times provided in the [Flow Chart](#).

To achieve a stable heart rate at rest and to assure high quality recordings, the site personnel will be instructed to assure a relaxed and quiet environment, so that all subjects are at complete rest.

All ECGs will be recorded for a 10 sec duration after subjects have rested for at least 5 min in a supine position. ECG assessment will always precede all other study procedures scheduled for the same time to avoid compromising ECG quality.

All ECGs will be stored electronically on the Muse CV Cardiology System ([REDACTED]). Electrode placement will be performed according to the method of Wilson, Goldberger and Einthoven.

All locally recorded ECGs will be evaluated by the investigator or a designee.

The investigator will assess the ECG recording as 'normal', 'abnormal - not clinically significant', or 'abnormal - clinically significant' and include a description of the abnormality as required. The ECG parameters assessed will include heart rate, PR, QRS, QT, and QTcF (calculated using Fridericia's method).

Abnormal findings will be reported as AEs (during the trial) or baseline conditions (at screening) if assessed to be clinically relevant by the investigator. Any ECG abnormalities will be carefully monitored and, if necessary, the subject will be removed from the trial and will receive the appropriate medical treatment.

ECGs may be repeated for quality reasons (for instance, due to alternating current artefacts, muscle movements, or electrode dislocation) and the repeated ECG will be used for analysis. Additional (unscheduled) ECGs may be collected by the investigator for safety reasons.

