### 7.3 PLANNED ANALYSES

#### 7.3.1 General considerations

Statistical analyses will be based on the following analysis sets:

- Treated set (TS):  
The treated set includes all subjects who were randomized and treated with at least one dose of study drug (i.e. verum or placebo). The treated set will be used for safety analyses
- Pharmacokinetic parameter analysis set (PKS):  
This set includes all subjects in the treated set (TS) who provide at least one PK endpoint that was defined as primary or secondary and was not excluded due to a protocol deviation relevant to the evaluation of PK or due to PK non-evaluability (as specified in the following subsection ‘Pharmacokinetics’). Thus, a subject will be included in the PKS, even if he/she contributes only one PK parameter value to the statistical assessment. Descriptive and model based analysis of PK parameters will be based on the PKS
- Pharmacodynamic parameter analysis set (PDS):  
This set includes all evaluable subjects from the TS who provide at least one evaluable pre- and post-dose measure for a PD endpoint. Descriptive and model based analysis of the PD endpoints will be based on the PDS

All individual data will be listed.

Adherence to the protocol will be assessed by the trial team. Important protocol deviation (IPD) categories will be specified in the iPD specification file prior to trial initiation, IPDs will be identified no later than in the Report Planning Meeting, and the IPD categories will be updated as needed.

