#### **4. CHANGES IN THE PLANNED ANALYSIS OF THE STUDY**

All analyses as planned in the CTP will be performed and are described in more detail in this TSAP. The following changes compared to the clinical trial protocol will be made:

The definition of the treated set was slightly adapted. The treated set will not be based on “randomized” subjects but will include all entered subjects who were treated with one dose of study medication.

For the second primary endpoint, a statistical model only including fixed effects was defined in the protocol. The statistical model used for the primary analysis was changed to a mixed model in order to take the repeated measures within each subject into account. Treatment group specific effects of CSF vs. plasma will be evaluated by including an interaction term of treatment group and the PK matrix to the model. The originally defined model will be computed as a sensitivity analysis.

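### SAP 7.8.4 follows the protocol's rule for reporting ECG findings but, without declaring it, drops the listing and descriptive summary of ECG intervals that the general rules call for

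*SAP*

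**What the plan says.** Protocol 2.2.2.2 opens with "Safety and tolerability of BI 474121 will be assessed based on" and gives four bases: adverse events, laboratory tests, 12-lead ECG and vital signs. SAP 5.2.2 repeats the list. Clinically relevant physical-examination findings are placed inside the adverse-event item. ECG has an item of its own.

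Protocol 5.2.4 makes the ECG quantitative: "The ECG parameters assessed will include heart rate, PR, QRS, QT, and QTcF". It also sets the reporting rule: "Abnormal findings will be reported as AEs (during the trial) or baseline conditions (at screening) if assessed to be clinically relevant by the investigator". Protocol 7.3.5 restates that rule briefly for the analysis.

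The general rules are wider. Protocol 7.3.1 says "All individual data will be listed", with no exception for ECG. Protocol 7.3.5 has continuous safety data tabulated with descriptive statistics, and has vital signs or other safety-relevant data examined for on-treatment change from baseline. SAP section 7 says that individual values of all subjects will be listed.

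SAP 7.8.4 sends clinically relevant ECG findings to medical history or baseline conditions if they arise at screening, and to adverse events if they arise on treatment. It ends with "No separate ECG listing will be provided" and plans no table. SAP section 4 states "All analyses as planned in the CTP will be performed and are described in more detail in this TSAP". The two changes it then declares concern the treated-set definition and the model for the second primary endpoint.

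**The concern.** A stated safety basis with measured, continuous values would reach the report only as investigator-selected findings. Protocol 4.1.5 says that the investigator knows the treatment in every part, so the one ECG outcome in the report is a treatment-aware judgement with no interval values beside it. A reader of the report could not see PR, QRS, QT or QTcF by dose.

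The protocol itself gives weight to these data. Exclusion criteria 11, 20 and 21 concern QT prolongation or its risk factors, and Section 3.1 includes ECG in the minimum safety data for moving from 20 mg to 40 mg.

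The omission is also undeclared. Someone relying on SAP section 4 would conclude that ECG is analysed as the protocol planned.

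**Working it through.** No formula or stated figure is at issue. The check compares the documents and counts the data affected.

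**Step 1. Treatment of the four safety bases in the SAP.**

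| Basis | Relevant findings become AEs | Descriptive summary | Individual listing |
|---|---|---|---|
| Adverse events, including physical examination | not applicable | frequency tables (7.8.1) | under the general rule in section 7 |
| Laboratory | yes (7.8.2) | by planned time, with change from baseline (7.8.2) | yes, with flags (7.8.2) |
| Vital signs | yes (7.8.3) | by planned time, with change from baseline (7.8.3) | yes, with difference from baseline (7.8.3) |
| ECG | yes (7.8.4) | none | ruled out (7.8.4) |

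Laboratory and vital-sign findings also become AEs when clinically relevant, and they are still listed and summarised. AE reporting therefore does not replace a listing elsewhere in this SAP.

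**Step 2. Which protocol rules are met.**
- AE or baseline-condition reporting of relevant findings (Protocol 5.2.4 and 7.3.5): met.
- Listing of all individual data (Protocol 7.3.1, and SAP section 7): not met for ECG.
- Descriptive statistics for continuous safety data (Protocol 7.3.5): not met for ECG.
- Change from baseline for other safety-relevant data (Protocol 7.3.5): not met for ECG. AEs, laboratory data and vital signs are each named in 7.3.5, so ECG is the only one of the four bases left for that phrase to cover.
- Declaration in SAP section 4: absent.

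**Step 3. Size.** As extracted, the Flow Chart shows four ECGs per subject: screening, Day -1, 48 h and end of trial (Day 8 to 14).
- Subjects if all parts run: 4 (placebo) + 4 (2.5 mg) + 4 (10 mg) + 6 (20 mg) + 6 (40 mg) = 24.
- Scheduled tracings: 24 × 4 = 96. With five parameters each: 96 × 5 = 480 values.
- Post-dose tracings: 24 × 2 = 48.
- SAP Table 6.1: 2 ends the on-treatment phase at 168 h, and Day 8 minus Day 1 is 7 × 24 = 168 h. The end-of-trial ECG therefore falls in follow-up, apart from a Day 8 visit held before the clock time of dosing. That leaves the 48 h ECG: 24 × 1 = 24 tracings and 24 × 5 = 120 values.

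The column alignment of the extracted Flow Chart is imperfect. Protocol 3.1 asks for ECG data up to at least 24 h before escalation, while the extracted chart shows no ECG between dosing and 48 h. The count should be confirmed against the original chart.

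**The case against.** The strongest reply is that a specific rule governs a general one. The only sentence in Protocol 7.3.5 that names ECG reports relevant findings as AEs, Protocol 5.2.4 says the same, and SAP 7.8.4 repeats it. This stands as far as it goes. A reader might infer that SAP 7.8.4 as a whole contradicts the protocol, and the documents do not support that: AE reporting on the investigator's judgement is the protocol's own rule. But the sentence does not say that AEs are the only output, and the same reporting route does not displace listings for laboratory data or vital signs.

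Other stronger readings also fail:
- That only AEs are reported. Relevant screening findings are listed as baseline conditions.
- That a shift in heart rate would go unseen. SAP 7.8.3 tabulates pulse rate with change from baseline, and the Flow Chart schedules vital signs several times on Day 1.
- That 450 ms is a limit below which a QTcF change escapes reporting. It is an eligibility mark at screening (exclusion criterion 20). Protocol 5.2.4 sets no numeric cut-off for an abnormal ECG.
- That "the repeated ECG will be used for analysis" promises a table. It says which tracing counts when one is repeated for quality reasons.

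It is also fair to say that one 48 h value per subject, in groups of 4 to 6 and with no power basis, says little about a dose-related effect. That limit comes from the schedule and the sample size, and a table would not remove it. It lowers the value of the summary but does not resolve the conflict over the listing.

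**Conclusion.** The point holds as a minor one. SAP 7.8.4 meets the protocol's ECG-specific reporting rule. It omits, without declaring it, the individual listing and the descriptive and change-from-baseline assessment that the protocol's general safety rules call for, and it conflicts with the SAP's own listing rule. Up to 96 tracings would go unlisted. Up to 24 on-treatment tracings, and the follow-up tracings after them, would go unsummarised.

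This rests on three assumptions: that all trial parts run, that the Flow Chart is as extracted, and that no redacted part of the SAP plans an ECG summary (7.8.4 itself reads as complete). The documents do not show that a QTcF effect would otherwise be found. The gain is that a stated safety basis could be described by dose.

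**What to change.** In SAP 7.8.4:
- Replace the exclusion with a listing of heart rate, PR, QRS, QT and QTcF by subject and planned time.
- Add one table by treatment of value and change from the last pre-dose ECG at 48 h, with the end-of-trial ECG shown separately as follow-up.
- Keep the reporting of clinically relevant findings as AEs or baseline conditions.
- State that the table is descriptive and that, with the first post-dose ECG at 48 h, it cannot exclude an earlier QTcF effect.

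The cost is one listing and one small table. Protocol 5.2.4 says the ECGs are stored electronically, but the documents do not say that the intervals are in the trial database. If they are not, they must be transferred and checked, which is the main expense.

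If the sponsor prefers not to do this, the minimum is to declare and justify the omission in SAP section 4 and to reconcile the listing rules in Protocol 7.3.1 and SAP section 7 with SAP 7.8.4.
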